## **7.3 Treatment Period**

Participants are expected to use the CKT or QG apps for 8 weeks after randomization. During a period of 8 weeks, the user will be able to use all of the features of CKT or QG to help them quit smoking. Participants will have an adherence check at Week 4 (Day 28) to encourage user engagement adherence and to confirm the Smokerlyzer is in proper working condition. Participants will be notified via SMS and email at Week 4 (Day 28) to submit their CO assessment.

Failure CO assessment submission at the 4-week compliance check will not be considered a protocol deviation, but only recorded as a study data point. However, if the CO assessment submission for adherence is not received at Week 4 (Day 28), the research coordinator will begin the follow-up procedure (Section 6.3) on Day 29 (Day 1: Text; Day 2: Text 2; Day 3: F/U Phone Call). Day 53: Participants will be sent a link to complete the end of study assessments (outcome survey +CO assessment) via SMS and email. A link to the Smokerlyzer video instructions will also be provided on Day 53. At the end of treatment on Day 56, a reminder SMS and email will be submitted to the participants who have not completed the EOS assessments. A link to the outcome survey will also be provided for the participants that have not submitted prior to Day 56.

#### **7.4 Study Completion**

Study termination letters will be emailed or mailed to participants upon loss to follow up or upon study completion (completion of the Outcome Survey).

Additionally, all participants that were randomized into the clinical trial will be emailed or mailed documentation revealing the study sponsor as “Click Therapeutics” along with a brief explanation of the sponsor’s masking rationale. (See Appendix **15.14**).

There will be no long-term follow-up of users after the 8-week outcome survey is completed.

#### **7.5 Schedule of Assessments**

The study schedule of activities is as follows:

| Protocol Activity     | Screening      | Baseline | Randomization | Treatment |        |
|-----------------------|----------------|----------|---------------|-----------|--------|
| Study Treatment Day   | -28 — -7       | -7 — -1  | 0             | 28        | 56     |
| End of Week           | Weeks -4 to -1 | Week 0   | Week 1        | Week 4    | Week 8 |
| Informed Consent      | X              |          |               |           |        |
| Eligibility Criteria  | X              | X        | X             |           |        |
| Baseline Survey       |                | X        |               |           |        |
| Randomization         |                |          | X             |           |        |
| Adherence Check       |                |          |               | X         |        |
| Primary Endpoints     |                |          |               |           |        |
| Outcome Survey        |                |          |               |           | X      |
| Exhaled CO Assessment |                |          |               |           | X      |

## 7.6 Screening Period

Screening procedures will occur online where individuals will be asked several basic questions to determine study eligibility for participation. (See Appendix 15.2) If answers indicate eligibility, the user will be prompted to complete the informed consent. Upon consent, the user will be emailed a personalized link to complete the baseline survey.

The below information/assessments will be collected during the screening period:

- Eligibility Questionnaire via Magellan / social media advertisement
- Informed Consent must be digitally signed and dated by the participant prior to any baseline assessments or any study-related assessments (participants should contact the study coordinator via phone or email with any questions about the study or consent prior to signing the consent form). Upon completion of the online Informed Consent, a copy of the signed ICF will be provided to the participant.
- Assign participant unique user ID number
- A personalized link that can be traced back to the user ID will be sent to the participant to complete the baseline survey.

## 7.7 Baseline Period (0-10 days prior to Randomization)

Once the personalized link to the baseline survey is sent to the participant, the participant has a 7-day window to complete the baseline survey and a 3-day window to complete a phone call with the research coordinator that is contingent upon completion of the baseline survey. This phone call serves as a secondary measure to confirm eligibility once more before participant can be randomized. Completion of the baseline survey will prompt the participant to schedule the randomization phone call with the study coordinator via Calendly.

## **7.8 Randomization (Day 0 of treatment period)**

Once the baseline survey has been completed and the phone call between the participant and study coordinator has been scheduled, the next step is randomizing the participant over the phone call. During this phone call, the participant is randomly assigned to an application by receiving a link to download the application via email from the research coordinator. Those who are not able to complete the study procedures by confirming successful download of the application over the phone call with the study coordinator will be considered a screen failure and not included in the ITT sample.

The following information/assessments will be collected at the randomization phone call:

### **Step 1: Research coordinator confirms eligibility and randomizes**

- Study coordinator reviews baseline questionnaire answers with participant to confirm eligibility
- After study eligibility is confirmed, the study coordinator will randomize the participant into one of the two treatment groups (Clickotine or QuitGuide)
- The assigned treatment and iCO Smokerlyzer application links will be emailed to the participant for download. The study coordinator will provide step-by-step application download instructions for the participants over the phone call and explicitly written out in the email. The participants who are randomly assigned to Clickotine will receive an access code in the email that contains the application download instructions because Clickotine requires a valid access code for the user to partake in the program.

### **Step 2: Participant confirms success or failure of application download**

- Participant confirms or denies successful installation of both the treatment application and iCO Smokerlyzer application. Successful application download initiates Day 0 of the treatment (intervention) period.

**Step 3: Site Investigator or Site Staff mails CO assessment device**

- Research coordinator confirms participant address to mail the iCO Smokerlyzer device after study start date/successful app installation is confirmed. The participant may use the Smokerlyzer at their own discretion but are encouraged to use the device throughout the study.
- Participant “Welcome Letter” via SMS & email including a link to the Smokerlyzer video instructions

**7.9 Smokerlyzer Confirmation Assessment (Week 4/ Day 28)**

Participants will be notified to submit Smokerlyzer assessment via SMS & email at Week 4 (Day 28). A link to the Smokerlyzer Instruction video will also be provided. Smokerlyzer receipt and functioning will be confirmed by having the participant submit an exhaled CO assessment via their iCO Smokerlyzer and recorded in the study database as “Yes” or “No”

The following information/assessments will be collected at Day 28:

**Compliance check:**

- Participants will submit exhaled CO assessment via their iCO Smokerlyzer
- Verify Participant received Smokerlyzer
- Verify Smokerlyzer is in working condition

**Participants will:**

- Continue to use Clickotine® or QuitGuide as instructed
- Continue their smoking cessation medication or NRT, if applicable
- Complete and submit exhaled CO assessment

**7.10 Study Outcome Assessment (Day 53 – 59)**

Participants will be notified at Day 53 via SMS and email to complete the 8-Week Study Outcome Survey + iCO Smokerlyzer CO assessment. The target completion date for the study outcome survey is at Day 56; however, the participants will be sent a link to the Outcome Survey via SMS and email at Day 53.

Study participants will have 7 days from Day 53 to complete the EOS assessments. An additional SMS and email reminder (SMS and & email) to complete EOS assessments will be sent to the participants who have not submitted the EOS assessments on Day 56. In the event that the study

outcome assessments are not submitted by Day 56, the research coordinator will intervene per the protocol outlined end of study follow-up attempts procedure (Section 6.3)

The following information/assessments will be collected at the participant end of study (Day 53-59):

**Outcome Survey:**

- Link to survey will be sent via email and SMS
- After a participant completes the outcome survey a linked CO assessment reminder will be automated.
- Participants will report any smoking cessation medication or NRT use

**Exhaled CO assessment:**

- Participants will submit exhaled CO assessment via their iCO Smokerlyzer
- Participants will have the opportunity to conduct the CO assessment via live video monitoring to confirm identity
- The assessment will be used to compare CO measurement with self-report data

At Day 56, if the participant has already completed the Outcome Survey and submitted their exhaled CO assessment, they will receive an EOS: Thank you letter (*Appendix 15.13.*) via SMS and email. If the participant has not completed the Survey or CO assessment the study coordinator will then intervene as per the protocol outline follow-up attempts procedure (*Section 6.3*).

On Day 59, the trial period ends, and the Outcome Survey link will expire at the end of the day. Participants who have not completed the Survey or CO assessment after the follow-up attempts procedure will be considered as a Lost to Follow-up participant.

## **7.11 Withdrawal Criteria/ Participant Withdrawal**

Participants will be instructed that they are free to withdraw from the study at any time without penalty or implications for any healthcare they receive. Participants who terminate the study early for any reason will be considered withdrawn.

Participants who were randomly assigned and withdraw from the study will not be replaced, regardless of the reason for withdrawal. If a participant does not complete a scheduled or required assessment or survey, every effort should be made to contact the participant. In any circumstance, every effort should be made to document participant outcome, if possible.

Reasonable efforts will be made by the research coordinator to retain participants in the study and to complete study assessments within protocol specified timeline. In the event a participant misses a required activity or assessment, follow-up efforts will include outreach via SMS, email, and phone-per the protocol follow-up procedure (Section 6.3).

If the participant withdraws from the study, and also withdraws consent for disclosure of future information, no further evaluations should be performed, and no additional data should be

collected. The sponsor may retain and continue to use any data collected before such withdrawal of consent. Subjects who do not complete the final outcome survey at 8 weeks will be considered Lost to Follow-Up and will not receive any compensation for participation. Subjects will receive payment for all completed study assessments after submission of the outcome survey at week 8.

## **8. ASSESSMENTS**

### **8.1 Smokerlyzer Confirmation Assessment (Week 4 / Day 28)**

SMS messages are delivered to promote participant adherence and regular app use. Both treatment conditions will receive messages with links to required surveys and assessments as they become available.

The Smokerlyzer confirmation assessment will take place at Week 4 (Day 28). Adherence will be assessed by having the participant submit an exhaled CO assessment via their iCO Smokerlyzer recorded as a study data point of “Yes” or “No” for the participant adherence check. The research coordinator will be able to monitor participant receipt of the iCO Smokerlyzer and also verify the Smokerlyzer device is in proper working condition prior to the EOS.

At the time of the Outcome Survey, participants will be asked to submit another exhaled CO assessment to compare value with self-report data.

### **8.2 Outcome Assessment**

At the end of the 8-week period users will be contacted to complete the web-based 8-week outcome survey and submit the remote CO assessment (See Appendix 15.4). The link for the outcome survey will be sent via SMS & email at Day 53. After the outcome survey is submitted, the participant will be reminded to complete the exhaled CO assessment.

At Day 56, if the participant has completed the Outcome Survey and submitted their exhaled CO assessment, they will receive an end of study thank you letter via SMS & email (Appendix 15.13).

An additional EOS reminder will be sent on Day 56 to participants via SMS and email.

The EOS reminder will include a survey link for the participants that have not submitted the outcome survey. If the outcome survey or CO assessment is not submitted by Day 56, protocol EOS follow-up procedure (Section 6.3) will start. Participants will receive a phone call follow-up at Day 58 for the last reminder to complete the EOS assessments.

## **CONFIDENTIAL**

After Day 59, the Outcome Survey link will close and the trial period ends. Participants who have not completed the Survey or CO assessment will be considered Lost to Follow-up. Participants that are deemed lost to follow-up will also receive a separate EOS: Thank-You / Lost to follow-up Letter (Section 15.15).

Participants will receive EOS: Thank you letter upon completion of outcome assessments or after the trial period ends / outcome survey link is expired.

A portion of the study populations that completes the outcome survey will be invited to conduct the CO assessment via live video monitoring to confirm identity. Participants that are invited to conduct the CO assessment via live video monitoring will consent to participate in live video monitoring at the end of the outcome survey by answering “Yes” or “No”. Study participants that answer “Yes” will then select their preference of video platform and will then be linked to schedule a video call via Calendly with the research coordinator.

Those who do not consent to participate in the live video monitoring CO assessment will then receive the automated reminder to submit the end of study remote CO assessment. After 25 videos are received from each group, participants will no longer be invited to submit the CO assessment over live video feed.

Study participants will have the opportunity to receive up to \$150 (Amazon Gift Certificate) at the end of study completion / Week 8. The participant will be rewarded a \$50 Amazon gift certificate in return for completing each of the following activities/assessments:

*\$50- Outcome Survey*

*\$50- CO Assessment Submission*

*\$50- CO Assessment via Live Video Monitoring*

Subjects will receive a separate \$50.00 Amazon Gift Certificate payment for each completed study activity/assessment that is submitted. The clinical research coordinator will provide the \$50.00 Amazon gift certificates via email after submission.

### **8.3 Assessment of Efficacy**

To assess 30-Day Sustained Abstinence from Smoking (NACQ, 2016) participants are asked the following questions in the Outcome Survey to determine Russell Standard Self- Reported 4-Week Quitter status (West et al., 2005):

1. Have you smoked (even a puff) in the last 30 days?

- a. Yes
- b. No

2. (If yes, this question will appear) Have you smoked (even a puff) in the last 14 days?
  - a. Yes
  - b. No
3. (If yes, this question will appear) Have you smoked (even a puff) in the last 7 days?
  - a. Yes
  - b. No

The Outcome Survey will instruct subjects to submit an exhaled carbon monoxide (CO) reading with the iCO Smokerlyzer they were mailed after participant randomization. iCO Smokerlyzer devices will be programmed to email the exhaled carbon monoxide measurement results to the research coordinator directly.

The primary outcome, 30-day abstinence from smoking, will be assessed via self-report on the outcome survey. Confirmation with the remote CO assessment will be conducted to assess concordance between self-report and remote CO assessment results. Abstinence as per the CO assessment will be defined as an iCO reading of fewer than 7ppm exhaled CO.

### **Fagerstrom Test for Nicotine Dependence**

The Fagerstrom Test for Nicotine Dependence is used to quantify the severity of nicotine dependence in smokers. This test is also used to determine if a participant may need additional assistance in quitting smoking with a Nicotine Replacement Therapy (NRT) or medication.

The Fagerstrom score is used to determine nicotine replacement therapy recommendations based on the participants nicotine dependence total score. In scoring the Fagerstrom Nicotine Dependency Test, yes/no items are scored from 0 to 1 and multiple-choice items are scored from 0 to 3. The items are added to yield a total score of 0-10. The higher total Fagerstrom score indicates a more intense/ higher dependency to nicotine (Heatherton, et. al, 1991). The test is administered at both the Baseline Survey and at the 8-week Outcome Survey (FTND only administered at the 8-week Outcome survey based on the participants self-report smoking status)

To evaluate nicotine dependence, participants are asked the following questions from the Fagerstrom Test for Nicotine Dependence (Heatherton, et. al, 1991):

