## **6.4 Permitted Concomitant Treatments**

To control for medication or NRT use, participants will not be eligible to enroll if they are currently using a medication or NRT at study enrollment.

Starting at Day 0 of the study, study participants will be allowed to choose to begin using a smoking cessation medication or NRT. Participants will be asked about medication or NRT use during the study in outcome survey.

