### 8.4 Assessment of Level of Risk

This study presents minimal risk, as the interventions do not involve any invasive or risky medical procedures and can be considered no greater risk than ordinarily encountered in daily life. The potential benefit of study participation includes successful smoking cessation. Although documented risks of smoking cessation apps have rarely if ever been demonstrated, potential risks may be considered minimal and no greater than those associated with standard of care behavioral therapies for smoking cessation. In this context, the benefit-risk balance for study participation is considered highly favorable. Furthermore, this trial will ascertain potential adverse events via medical monitoring procedures and will be conducted in compliance with the protocol, good clinical practice (GCP), and the applicable regulatory requirements.

Both Clickotine and QuitGuide were developed to follow US Clinical Practice Guidelines for smoking cessation interventions. Use of either app may produce risks caused by the nicotine withdrawal associated with any attempt to quit smoking, including irritability and insomnia. Both QuitGuide and Clickotine are commercially available apps. Neither includes manufacturer's safety warnings nor involves any medical recommendations regarding use of prescription or over the counter quit aids.

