#### **10.4 Secondary Endpoint**

Concordance rates between self-reported 30-day abstinence and the remote CO monitoring result will be estimated, with concordance > 85% considered evidence of a valid reporting process by Magellan Behavioral Health. Concordance rates will be compared between users that submit the CO measurement under video monitoring and those that do not. Upon completion of the Outcome Survey, participants will be invited to submit the CO assessment over a live video feed to confirm identity, until videos are received from 25 CKT users and 25 QG users. After 25 videos are received from each group, participants will no longer be invited to submit the CO assessment over live video feed.

Secondary analysis of the subgroup of NRT/pharmacotherapy users will be conducted to compare cessation rates between the CKT+NRT group and the CKT-only group, to confirm the initial trial result that CKT+NRT is not superior to CKT-alone.

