# **12. ETHICS**

## **12.1 Regulatory Considerations**

As this study utilizes solely commercially available Apple iPhone and Google Play Store devices, and does not involve any medical recommendations regarding use of prescription or over the counter quit aids, this study is subject to Investigational Device Exemption (IDE).

This study is funded by a National Institute of Health, National Institute of Drug Abuse grant 1 R43 DA045395-01 “Clinical trial of an innovative digital therapeutic for smoking cessation with biochemical verification” to [name]. The PI will seek NIDA prior approval for any significant changes proposed to the protocol. All Western IRB actions relevant to the study, including changes or amendments to the study protocol, will be communicated to NIDA.

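### The protocol says in 8.3 that the Fagerstrom score determines NRT recommendations and in 12.1 that the study makes none; separately, CKT+NRT is compared with CKT-only with no stated adjustment for dependence

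*Protocol*

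**What the plan says.** **Recommendations on quit aids.** Under the Fagerstrom heading in Protocol 8.3, the test has a second use: "This test is also used to determine if a participant may need additional assistance in quitting smoking with a Nicotine Replacement Therapy (NRT) or medication". In the next paragraph it adds: "The Fagerstrom score is used to determine nicotine replacement therapy recommendations based on the participants nicotine dependence total score". Protocol 12.1, speaking of the study, says that it "does not involve any medical recommendations regarding use of prescription or over the counter quit aids, this study is subject to Investigational Device Exemption (IDE"). Protocol 8.4, repeated in the SAP under Trial Safety, speaks of the two apps: "Neither includes manufacturer's safety warnings nor involves any medical recommendations regarding use of prescription or over the counter quit aids". Protocol 1.2 lists advice on pharmacotherapy among the guideline features that Clickotine is designed to deliver.

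**Use of quit aids.** Protocol 6.4 says that from Day 0 "study participants will be allowed to choose to begin using a smoking cessation medication or NRT". Protocol 2.2 and the SAP's protocol summary agree.

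**Analysis.** Section 10.4 of both documents, and the SAP's Data Analysis Plan, will "compare cessation rates between the CKT+NRT group and the CKT-only group, to confirm the initial trial result that CKT+NRT is not superior to CKT-alone". None of the three places names a model, covariates or a margin for this comparison. Nicotine dependence appears as a covariate only with the 30-day cessation comparison of CKT against QuitGuide (10.3 of both documents, and the Data Analysis Plan).

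**The concern.** There are two points, and the second does not depend on the first.

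1. A reader cannot tell whether participants are given quit-aid recommendations based on their score. 8.3 says the score has that use, and 12.1 says the study involves no such recommendations. The second pair is similar: 8.4 says the apps involve none, while 1.2 lists advice on pharmacotherapy among the features of one of them.

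2. CKT+NRT against CKT-only is a comparison of self-selected groups inside one randomised arm. Dependence plausibly affects both the choice to use NRT and the chance of quitting. If heavier dependence goes with more NRT use and less quitting, the crude difference is pulled down, towards the result that the plan says it expects to confirm. A real benefit of adding NRT could then look like none, on a stated secondary objective.

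**Working it through.** **The passages side by side**

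| Place | Subject of the statement | Content |
|---|---|---|
| Protocol 8.3 | the Fagerstrom score | determines NRT recommendations |
| Protocol 12.1 | the study | no recommendations on quit aids |
| Protocol 8.4, SAP Trial Safety | the two apps | no recommendations on quit aids |
| Protocol 1.2 | the Clickotine app | advice on pharmacotherapy among its features |
| Protocol 6.4, 2.2 | the participant | may choose to start NRT or medication |

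The conflicting pairs are 8.3 with 12.1, and 8.4 (with its SAP copy) with 1.2. Section 6.4 is a permission and conflicts with neither.

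**The plan's own figure.** The only size given is for the primary comparison: 26.2% against 8.3%, two-sided 0.05, 85% power, 78 per arm. With pooled variance, mean p = (0.262 + 0.083)/2 = 0.1725:

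n = [1.960 × √(2 × 0.1725 × 0.8275) + 1.036 × √(0.262 × 0.738 + 0.083 × 0.917)]² / 0.179² = 78.4, so 79 per arm.

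Power at 78 per arm is 84.8%. The stated figure reproduces, and nothing below changes it. No size or power is given for CKT+NRT against CKT-only.

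**Bias, hand-checkable version.** Assume that half the CKT arm is highly dependent, that the arm's abstinence is 26.2% (10.5), and that NRT has no effect. Take abstinence of 21.0% (high dependence) and 31.4% (low), and NRT uptake of 40% and 20%.

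- CKT+NRT: (0.40 × 0.210 + 0.20 × 0.314)/0.60 = 24.5%
- CKT-only: (0.60 × 0.210 + 0.80 × 0.314)/1.40 = 26.9%
- Crude odds ratio: (0.245/0.755)/(0.269/0.731) = 0.88, although the true value is 1

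With abstinence of 16.2% and 36.2% and uptake of 50% and 10%, the rates are 19.5% and 29.1%, odds ratio 0.59. With equal uptake in both strata it is 1.00.

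**Bias, using the score.** From the documents: pilot mean Fagerstrom score 6.1 (Protocol 1.3) and 26.2% quitting. Assumed: scores 0 to 10 as a discretised normal with SD 2.2, uptake changing at a score of 6, and a fixed fall in the log-odds of quitting per point. The intercept is solved to give 26.2% overall.

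| Uptake at 6 or more / below 6 | True OR | Crude OR at slope −0.1 / −0.2 / −0.3 |
|---|---|---|
| 40% / 10% | 1.5 | 1.32 / 1.15 / 1.00 |
| 40% / 10% | 1.0 | 0.88 / 0.78 / 0.68 |
| 50% / 20% | 1.5 | 1.34 / 1.20 / 1.07 |
| 50% / 20% | 1.0 | 0.90 / 0.81 / 0.73 |
| 30% / 20% | 1.5 | 1.43 / 1.36 / 1.28 |
| 30% / 20% | 1.0 | 0.96 / 0.92 / 0.88 |

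In the first case 28% of participants use NRT, and users score 1.2 points higher on average than non-users.

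**Precision.** Expected CKT quitters: 78 × 0.262 = 20.4. The 95% half-width for the difference is 1.96 × √[0.262 × 0.738 × (1/m + 1/(78 − m))], where m is the number of NRT users.

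| Assumed NRT share | Users / non-users | Half-width |
|---|---|---|
| 10% | 8 / 70 | 32 points |
| 20% | 16 / 62 | 24 points |
| 30% | 23 / 55 | 21 points |
| 50% | 39 / 39 | 20 points |

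**The case against.** Much can be said against pressing this harder, and most of it stands.

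- **A reader might infer that co-treatment is written two ways.** It is not. The permission is consistent throughout, and freedom to choose NRT is compatible with receiving a recommendation. 8.4 speaks of the apps, so it does not directly contradict a study-level use of the test.
- **A reader might infer that quit aids go by rule to the more dependent, perhaps on the randomisation call,** where the coordinator goes through the baseline answers. The stated purpose of that review is eligibility. The plan gives no cut-off, timing, wording or responsible person, and no call step, email, SMS or voicemail text delivers a recommendation. 8.3 may only describe the instrument in general. It does not say so, which is why the wording still needs reconciling.
- **A reader might infer that the confounding follows from the contradiction.** It does not. NRT use is self-chosen, so dependence can confound the comparison even if the 8.3 sentence is deleted. Acting on that sentence would only strengthen the effect.
- **The size is mostly assumption.** Only 6.1 and 26.2% come from the documents. Other self-selection, such as motivation, could push the other way.
- **Small numbers are the larger problem.** With about 22 users and 56 non-users, and rates of roughly 32% and 24% (odds ratio about 1.5), the half-width is about 22 points and power about 11% with no confounding at all. Adjustment does not cure that. Nor does it cure the outcome survey asking about current quit-aid use, so that someone who used NRT and stopped may be counted as CKT-only.

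None of this answers the remaining gap: the plan intends to confirm a finding from self-selected groups and states no adjustment for a measured, obvious confounder. Silence is not a statement that the analysis will be crude, but the comparison should not be left open.

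**Conclusion.** Both points hold at modest weight.

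1. Protocol 8.3 conflicts with 12.1, and 8.4 with its SAP copy sits badly with 1.2. This is a matter of wording to be reconciled. The documents do not show that any score-based recommendation is delivered.

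2. The CKT+NRT against CKT-only comparison is non-randomised and has no stated adjustment for dependence. If more dependent smokers use NRT more and quit less, it is biased towards the stated expectation. Over the assumptions shown, a true odds ratio of 1.5 appears as about 1.4 down to 1.0, and a true 1.0 as 0.96 down to 0.68 (0.59 in the most extreme two-group case). With a half-width of roughly 20 to 32 points, a crude or an adjusted result could not confirm that the combination is not superior.

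It would be going too far to say that the primary result is threatened. The Fagerstrom items are answered before randomisation, nothing in the plan applies a recommendation differently by arm, and the 78 per arm reproduces. The randomised comparison and its sample size are not affected.

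**What to change.** **Wording.** Reconcile Protocol 8.3 with 12.1, and Protocol 8.4 and the SAP's Trial Safety text with 1.2, so that the documents make one statement on whether the study or the apps give quit-aid recommendations. Which statement stands is for the sponsor to decide.

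**Analysis.** In section 10.4 of both documents, and in the SAP's Data Analysis Plan, state that cessation in CKT+NRT and CKT-only will be compared by logistic regression adjusted for the baseline Fagerstrom total score as one continuous covariate. Report the odds ratio with its 95% CI as an exploratory, non-randomised estimate, and drop the aim of confirming that the combination is not superior.

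**Cost.** A few sentences, with no added patients, visits or procedures, since the baseline score is already collected and nicotine dependence is already a covariate in the primary model. The price is one extra coefficient with about 20 expected CKT quitters. Confounding by anything other than measured dependence, and the wide interval, will remain and should be stated with the result.
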